11.5.2 Safety

Vital signs

All vital signs data will be listed by treatment sequence, subject, and visit/time and if ranges are available abnormalities (and relevant orthostatic changes) will be flagged. Summary statistics will be provided by treatment and visit/time.

ECG evaluations

All ECG data will be listed by treatment sequence, subject and visit/time, abnormalities will be flagged. Summary statistics will be provided by treatment and visit/time. Summary table for percentage and number of subjects with abnormal values <40 /40-90 />90 bpm in heart rate and summary table for percentage and number of subjects with notable values increase >30 / increase >60 / >450 />480/>500 msec in QTcF interval will be provided.

Clinical laboratory evaluations

All laboratory data will be listed by treatment sequence, subject, and visit/time and if normal ranges are available abnormalities will be flagged. Summary statistics will be provided by treatment and visit/time.

Summary table for percentage and number of subjects with notable values for serum potassium (<3 /3-<3.5 />5.5 mmol/L) and plasma glucose (>10-15 />15 mmol/L) will be provided.

Adverse events

All information obtained on adverse events will be displayed by treatment and subject.

All study emergent adverse events will be summarized. Adverse events starting on or after the time of the first inhalation of study drug will be classified as a treatment emergent adverse event. Any adverse events that started during a washout period will be assigned to the treatment period just prior to that washout period. Any adverse events that started during the study before the time of the first inhalation of study drug of the first period will be classified as a prior adverse event.

The number and percentage of subjects with treatment emergent adverse event summaries will be produced, overall by system organ class and preferred term, overall by system organ class, preferred term and maximum severity, suspected drug-related adverse events by system organ class and preferred term, serious adverse events by system organ class and preferred term, and adverse events leading to permanent discontinuation of study drug by system organ class and preferred term with a breakdown by treatment. A subject with multiple adverse events within a body system and treatment period is only counted once towards the total of this body system and treatment.

Concomitant medications / Significant non-drug therapies

All concomitant therapies will be listed by treatment sequence and subject.

11.5.3 Pharmacokinetics

Statistical methods for pharmacokinetic analysis

The log transformed pharmacokinetic parameters AUC0-24h,ss and Cmax,ss on day 14 will be compared for indacaterol acetate (test) relative to indacaterol maleate (reference) using a mixed effects model with sequence, treatment and period as fixed effects and subject nested within sequence as random effect. Body weight assessed in period 1 may be included as a covariate and applied as a fixed effect in the model. The estimates of the treatment differences (indacaterol acetate (test) vs. maleate (reference); Frel) along with their 90% confidence intervals will be obtained. The estimates and confidence intervals will be transformed back to the original scale to provide ratios of the geometric means together with their corresponding 90% confidence intervals.

Tmax,ss will be analyzed using non-parametric methods. The median difference and the 90% confidence interval of the median difference in Tmax,ss will be estimated using Hodges-Lehmann estimation procedure.

Handling of missing values/censoring/discontinuations

All subjects with evaluable PK parameters data for at least one study treatment will be included for this analysis

Summary statistics for pharmacokinetic data

Indacaterol plasma concentrations will be listed by treatment sequence, subject, profile day, and sampling time point. Descriptive summary statistics will be provided by treatment, profile day, and sampling time point. Summary statistics will include mean (arithmetic and geometric), SD, CV (arithmetic and geometric), median, minimum and maximum. Concentrations below LLOQ will be treated as zero in summary statistics. A geometric mean will not be reported if the dataset includes zero values.

Pharmacokinetic parameters will be calculated as described in [Section 8.7](#) (Pharmacokinetics) and will be listed by treatment sequence, profile day, and subject. Descriptive summary statistics will be provided by treatment and profile day. Summary statistics will include mean (arithmetic and geometric), SD, and CV (arithmetic and geometric), median, minimum and maximum. An exception to this is Tmax where median, minimum and maximum will be presented.

Graphical methods will be employed to show mean and individual time-concentration profiles. Pharmacokinetic parameters will be determined using WinNonlin Phoenix (version 6.4 or higher).

11.5.4 Pharmacokinetic / pharmacodynamic interactions

Not Applicable.

11.5.5 Other assessments

Not Applicable.

Corporate Confidential Information

11.7 Sample size calculation

Sample size calculations are based on the primary endpoint of trough FEV₁. Trough FEV₁ is defined as the average of the FEV₁ measurements at 23 h 15 min and 23 h 45 min post-dose.

The primary objective is to prove that the test formulation (the one included in the combination therapy which is acetate and maleate salt) must be better than placebo. Using an estimate of within subject standard deviation of 230 mL from Study QAB149D2301 and assuming the data are normally distributed, 42 (7 per sequence) subjects are required to detect the difference of 170 mL in trough FEV₁ with 90% power in each test (acetate vs placebo and maleate vs placebo).

No adjustment will be made for multiplicity because the objective is to obtain a statistical separation from placebo for both the comparisons.

The power where both tests are required to meet the overall objective is >81% power, with a two-sided test at a significance level of 5%.

Allowing for a 20% drop out rate, a total sample size of 54 (9 per sequence) subjects will be randomized to six treatment sequences.

11.8 Power for analysis of key secondary variables

The sample size was estimated based on the primary endpoint of trough FEV₁ is also adequate from a pharmacokinetic bioequivalence perspective. The intra-subject CV (coefficient of variation) of C_{max} and AUC_{0-24h} in Study CQAB149D2301 was 14% and 20%, respectively. Assuming a maximum intra-subject CV of 20% for AUC_{0-24h} (based on 7-day dosing in asthma subjects in Study CQAB149D2301), a sample size of 42 completers will provide at least 95% power to achieve [90% CI for geometric mean ratio (test/reference) within the interval of 0.80-1.25] with respect to the AUC_{0-24h,ss} of indacaterol, if the true geometric mean ratio is 1.

Corporate Confidential Information

12 Ethical considerations

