There was a marked increase in the incidence of cough 5 minutes after inhalation (as evaluated by direct and targeted observation by the investigator) of each of the indacaterol salts compared to placebo; the incidence rates following inhalation of indacaterol maleate, indacaterol acetate, indacaterol xinafoate, and placebo were 69%, 28%, 20%, and 7%, respectively. There was a significantly lower incidence of PI cough with the xinafoate and acetate salts in comparison to the maleate salt. The cough was characterized by a rapid onset, short duration and was predominantly mild to moderate in severity.

Study CQAB149D2301 was a multi-center, randomized, double-blind, placebo-controlled, multiple-dose, 4-way cross-over study consisting of four treatments namely indacaterol maleate, indacaterol xinafoate, indacaterol acetate (each at 400 µg) and matching placebo inhaled via the Concept1 device in 30 subjects with persistent asthma. Indacaterol, in all three salt forms, was well tolerated by subjects with no unexpected events observed and no subject having a serious adverse event. Only one subject was withdrawn from the study for severe adverse events that were not considered to be related to study drug. There were no clinically relevant changes in laboratory values or in ECG and vital signs. Cough within 5 minutes of dosing affected up to 59% subjects in the indacaterol maleate group. These coughs were mainly of moderate severity on day 1 but mainly mild thereafter. The incidence of cough was lower with the other two salts (14% patients in each group on Day 7).

Study CQMF149E2203 was a multicenter, randomized, double-blind, placebo-controlled, 12-week treatment, parallel-group study to assess the efficacy, safety, and pharmacokinetics of indacaterol acetate (75 and 150 µg o.d.) inhaled via the Concept1 device in patients with persistent asthma. Both indacaterol acetate treatment groups were safe and well tolerated. There were no deaths in this study. Besides one subject who discontinued the study due to an AE (asthma), there were no SAEs or discontinuations due to SAEs in the indacaterol acetate 150 µg group. The frequency of SAEs and discontinuations to AEs or SAEs was similar across the indacaterol acetate 75 µg and the placebo groups. The incidence of AEs and discontinuations from study was lower in indacaterol acetate 150 µg treatment group compared with the indacaterol acetate 75 µg and placebo groups.

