1.3.2.2 Indacaterol acetate

Study CQAB149D2301 was conducted with an early proof-of-concept type formulation (see [Section 1.3.1](#)). Following oral inhalation of 400 µg indacaterol via the Concept1, the pharmacokinetic profiles and systemic exposures of indacaterol acetate and indacaterol maleate in plasma were similar. The ratio of geometric means on Day 7 for AUC0-24h (acetate vs. maleate) was 0.975 [90% CI: (0.908, 1.046)] and for Cmax 0.976 [90% CI: (0.885, 1.077)]. This result showed that the PK profile for indacaterol was similar following oral inhalation as acetate or maleate via the Concept 1 device, which allowed for bridging to the existing human PK data for indacaterol maleate.

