1.3.3 Human pharmacodynamic data

1.3.3.1 Indacaterol maleate

A number of clinical trials have investigated the efficacy of inhaled indacaterol maleate in subjects with obstructive airway diseases, specifically asthma and COPD. A number of single and multiple dose dry powder and pressurized metered dose inhaler (pMDI) devices have been employed and doses of up to 3000 µg (single dose) and 800 µg (multiple dose for 28 days)/600 µg (multiple dose for 52-weeks) have been evaluated.

Data from an extensive clinical development program demonstrate that indacaterol maleate is an effective bronchodilator with a rapid onset and full 24 h duration of action in both asthma and COPD (approved indication for Onbrez® Breezhaler® (indacaterol maleate)). The bronchodilator effect data in subjects with asthma are also summarized below as this reflects the target population in this current study.

Indacaterol maleate in patients with COPD

Lung function

Onbrez® Breezhaler®, administered once a day at doses of 150 µg and 300 µg, demonstrated clinically meaningful improvements in lung function. At the 12-week primary endpoint (24-hour trough FEV₁), the 150 µg dose resulted in a 130-180 mL increase compared to placebo (p<0.001) and a 60 mL increase compared to salmeterol 50 µg twice a day (p<0.001). The 300 µg dose resulted in a 170-180mL increase compared to placebo (p<0.001) and a 100 mL increase compared to formoterol 12 µg twice a day (p<0.001). Both doses resulted in an increase of 40-50mL over open-label tiotropium 18 µg once a day (150 µg, p=0.004; 300 µg, p=0.01). The 24-hour bronchodilator effect of Onbrez® Breezhaler® was maintained from the first dose throughout a one-year treatment period with no evidence of loss in efficacy (tachyphylaxis) (Indacaterol (QAB149) IB).

Symptomatic benefits

Both doses demonstrated statistically significant improvements in symptom relief over placebo for dyspnea and health status (as evaluated by Transitional Dyspnea Index [TDI] and St. George's Respiratory Questionnaire [SGRQ], respectively). The magnitude of response was generally greater than seen with active comparators (salmeterol and tiotropium). In addition, patients treated with Onbrez® Breezhaler® required significantly less rescue medication, had more days when no rescue medication was needed compared to placebo and had a significantly improved percentage of days with no daytime symptoms.

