1.4 Study purpose

This study is designed to determine the steady-state pharmacodynamics, safety, tolerability, and systemic pharmacokinetics of indacaterol maleate 150 µg (the salt form used in the approved product Onbrez® Breezhaler®) and indacaterol acetate 150 µg (the salt form used in clinical development of QVM149 and QMF149 as a FDC with mometasone furoate) in subjects with asthma. The data from this study will support clinical development and registration of QMF149 and QVM149 by enabling bridging to the safety database of the approved monotherapy product, indacaterol maleate.

2 Study objectives and endpoints

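### Does the apparent swap of the AUC and Cmax variabilities from Study CQAB149D2301 undermine the PK power statement?

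*Protocol*

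**What the plan says.** Protocol 11.8 argues that the number of subjects chosen for trough FEV1 also suffices for PK equivalence. It reports that the within-subject CVs of Cmax and AUC0-24h, in that order, "in Study CQAB149D2301 was 14% and 20%, respectively". It then takes 20% as the maximum CV, assigns it to AUC0-24h ("based on 7-day dosing in asthma subjects in Study CQAB149D2301"), and claims at least 95% power with 42 completers for the 90% interval of the AUC0-24h,ss ratio to fall within 0.80 to 1.25 when the true ratio is 1. The readable text gives no matching figure for Cmax,ss. A redacted block follows 11.8, so nothing can be said about what stands there.

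Protocol 1.3.2.2 gives Day 7 acetate-to-maleate ratios from the same earlier study. The AUC0-24h ratio "was 0.975 [90% CI: (0.908, 1.046)] and for Cmax 0.976 [90% CI: (0.885, 1.077"). Protocol 1.3.1 describes that study as a four-way crossover, "inhaled via the Concept1 device in 30 subjects with persistent asthma". How many subjects were evaluable for PK is not stated.

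In the present trial both parameters are analysed. Protocol 11.5.3 says "The log transformed pharmacokinetic parameters AUC0-24h,ss and Cmax,ss on day 14 will be compared" between the two salts, and SAP 5.3 repeats this. Protocol 1.4 explains the purpose of the data: "enabling bridging to the safety database of the approved monotherapy product".

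**The concern.** In a crossover the width of a confidence interval on the log scale is proportional to the within-subject standard deviation. The wider interval should therefore belong to the parameter with the larger CV. Here it does not: 1.3.2.2 makes Cmax the noisier parameter and 11.8 makes it AUC. A reader who notices this cannot tell which section is right.

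Two things would seem to be at stake. First, if Cmax is really the more variable parameter, the readable power statement covers only the easier of the two comparisons. Second, the PK comparison supports the bridge from the acetate salt to the maleate safety data, so an error in its planning figures, or in the earlier PK evidence, deserves a check before it is dismissed.

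**Working it through.** **Inputs.** CVs of 14% (Cmax) and 20% (AUC), 42 completers, limits 0.80 to 1.25 and a true ratio of 1, all from Protocol 11.8. 90% intervals of 0.908 to 1.046 (AUC) and 0.885 to 1.077 (Cmax) from Protocol 1.3.2.2. At most 30 subjects, from Protocol 1.3.1.

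**1. The plan's own figure.** The log-scale SD is s = √ln(1 + CV²). For a CV of 20%, s = √ln(1.04) = 0.1980. The standard error of the log ratio is s·√(2/42) = 0.0432. With 40 df (42 − 2) the 90% half-width is about 1.684 × 0.0432 = 0.0728, against a margin of ln 1.25 = 0.2231. The room left is (0.2231 − 0.0728)/0.0432 = 3.5 standard errors on each side. Exact power of the two one-sided tests, integrating over the variance estimate, is 99.9%. The claim of at least 95% is true and conservative.

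**2. Is the order really reversed?**
- Log widths: ln(1.046/0.908) = 0.1415 for AUC and ln(1.077/0.885) = 0.1963 for Cmax. The ratio Cmax/AUC is 1.39 (1.37 to 1.41 allowing for rounding).
- CVs as labelled: s(14%)/s(20%) = 0.1393/0.1980 = 0.70.
- CVs with labels exchanged: 0.1980/0.1393 = 1.42.

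If both parameters were analysed in the same subjects, this comparison does not depend on how many there were.

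**3. Could different evaluable numbers explain it?** Inverting each interval gives s = [ln(U/L)/2] / [t·√(2/n)] and CV = √(exp(s²) − 1). The ranges below cover n − 2 df up to 3(n − 2), the residual df of a four-period crossover.

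| Assumed evaluable n | CV implied for AUC | CV implied for Cmax |
|---|---|---|
| 22 to 24 | 13.7–14.8% | 19.0–20.6% |
| 30 | 16.2–16.6% | 22.6–23.2% |

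With 30 subjects the AUC interval cannot imply a CV above 16.8%, even with the normal quantile in place of t. A CV of 20% for AUC would need about 43 or 44 subjects, more than the study had, and 14% for Cmax would need about 12 or 13. With the labels exchanged, both intervals fit a common n of about 22 to 24. That points to a swap in one of the two sections.

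**4. Does it matter?** Equivalence power with 42 completers and 40 df:

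| CV | True ratio 1 | True ratio 0.95 |
|---|---|---|
| 14% | >99.9% | >99.9% |
| 20% | 99.9% | 98.8% |
| 23.2% | 99.4% | 95.9% |

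Under the labels in 11.8, AUC sits in the 20% row and Cmax in the 14% row. With the labels exchanged they trade places. The 23.2% row is the least favourable reading of the intervals. Every entry in the ratio 1 column, which is the plan's own assumption, exceeds 95%; so does every entry at 0.95.

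**5. If 1.3.2.2 is the section in error.** The point estimates are 0.975 and 0.976, and both intervals lie well inside 0.80 to 1.25. Exchanging the names leaves the finding of similar exposure intact.

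**The case for a change.** The strongest argument for acting is that the two sections disagree on a matter of fact, that the data are meant for registration, and that a correction would cost a few words. The disagreement stands. It is more than loose wording, because no evaluable number up to 30 reconciles a 20% CV with the AUC interval. One qualification applies. The argument needs the CVs and the intervals to come from the same Day 7 analysis, and 11.8 does not say which treatments, day or model its CVs describe. In a study of three salts and placebo they could have come from a different fit. A swap is the natural explanation, but it is not proven.

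The missing Cmax power figure carries less weight. Power rises as the CV falls, so a calculation at the larger CV already covers the parameter with the smaller one, and an analyst reading 11.8 can draw that conclusion unaided. A separate Cmax sentence, or the evaluable number from the earlier study, would add detail without altering a decision. A power figure at 23% would bring in a CV that the protocol does not contain and that depends on assuming all 30 subjects were evaluable.

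One could also ask where the 170 mL in Protocol 11.7 comes from. That concerns FEV1, has no bearing on the PK labels, and is a request for a source and not an error: the value lies within the range in 1.3.3.1, where in COPD the 150 µg "dose resulted in a 130-180 mL increase compared to placebo".

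**Conclusion.** The mismatch is most likely a clerical slip: one pair of labels exchanged in either 1.3.2.2 or 11.8. It has no consequence for this trial. The power claim of at least 95% holds for both PK parameters under either labelling: 99.9% at a CV of 20%, and 99.4% at 23.2%, for a true ratio of 1 and 42 completers. The analysis in Protocol 11.5.3 and SAP 5.3 estimates its variance from the trial's own data and uses neither planning CV. The sample size comes from trough FEV1 in 11.7 and would not move.

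This rests on three assumptions: that the CVs and intervals describe the same analysis (needed only to call it a swap), that the evaluable number in the earlier study was no more than 30, and that within-subject variability here resembles that study's. The sponsor may tidy the labels against the earlier study's report when the text is next revised, but no change to design, analysis or interpretation depends on it.

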12.1 Regulatory and ethical compliance

This clinical study was designed and shall be implemented, executed and reported in accordance with the ICH Harmonized Tripartite Guidelines for Good Clinical Practice, with applicable local regulations (including European Directive 2001/20/EC, US Code of Federal Regulations Title 21, and Japanese Ministry of Health, Labor, and Welfare), and with the ethical principles laid down in the Declaration of Helsinki.

12.2 Responsibilities of the investigator and IRB/IEC

Before initiating a trial, the investigator/institution must obtain approval/favorable opinion from the Institutional Review Board/Independent Ethics Committee (IRB/IEC) for the trial protocol, written informed consent form, consent form updates, subject recruitment procedures (e.g. advertisements) and any other written information to be provided to subjects. Prior to study start, the investigator is required to sign a protocol signature page confirming his/her agreement to conduct the study in accordance with these documents and all of the instructions and procedures found in this protocol and to give access to all relevant data and records to Novartis monitors, auditors, Novartis Quality Assurance representatives, designated agents of Novartis, IRBs/IECs, and regulatory authorities as required. If an inspection of the clinical site is requested by a regulatory authority, the investigator must inform Novartis immediately that this request has been made.

For multi-center trials, a Coordinating investigator will be selected by Novartis around the time of Last Patient Last Visit to be a reviewer and signatory for the clinical study report.

12.3 Publication of study protocol and results

The key design elements of this protocol will be posted in a publicly accessible database such as clinicaltrials.gov. In addition, upon study completion and finalization of the study report the results of this trial will be either submitted for publication and/or posted in a publicly accessible database of clinical trial results.

13 Protocol adherence

This protocol defines the study objectives, the study procedures and the data to be collected on study participants. Additional assessments required to ensure safety of subjects should be administered as deemed necessary on a case by case basis. Under no circumstances is an investigator allowed to collect additional data or conduct any additional procedures for any research related purpose involving any investigational drugs under the protocol.

Investigators ascertain they will apply due diligence to avoid protocol deviations. If an investigator feels a protocol deviation would improve the conduct of the study this must be considered a protocol amendment, and unless such an amendment is agreed upon by Novartis and approved by the IRB/IEC and health authorities, where required, it cannot be implemented.

13.1 Protocol Amendments

Any change to the protocol can only be made in a written protocol amendment that must be approved by Novartis, Health Authorities where required, and the IRB/IEC prior to implementation.

Amendments that are intended to eliminate an apparent immediate hazard to subjects may be implemented immediately, provided the Health Authorities are subsequently notified by protocol amendment and the reviewing IRB/IEC is notified.

Notwithstanding the need for approval of formal protocol amendments, the investigator is expected to take any immediate action required for the safety of any subject included in this study, even if this action represents a deviation from the protocol. In such cases, the reporting requirements identified in [Section 9](#) (Safety monitoring) must be followed and the Study Lead informed.

14 References

Boxenbaum H, Battle M (1995) Effective half-life in clinical pharmacology. *J Clin Pharmacol* Aug;35(8): 763-6.

Global Initiative for Chronic Obstructive Lung Disease (GOLD); Global Initiative for Chronic Obstructive Lung Disease (2017 report).

Miller MR, Crapo R, Hankinson J, et al (2005a) General considerations for lung function testing. *Eur. Respir. J.* Jul;26(1): 153-61.

Miller MR, Hankinson J, Brusasco V, et al (2005b) Standardisation of spirometry. *Eur. Respir. J.* Aug;26(2): 319-38.

15 Appendix 1: Liver Event Definitions and Follow-up Requirements

Table 15-1 Liver Event and Laboratory Trigger Definitions

Definition	Thresholds
Potential Hy's law cases	
ALT or AST elevation with coagulopathy	
 ALT or AST $> 3 \times \text{ULN}$ and TBL $> 2 \times \text{ULN}$ without initial increase in ALP to $> 2 \times \text{ULN}$
ALT or AST elevation accompanied by symptoms	
 ALT or AST $> 3 \times \text{ULN}$ and INR > 1.5 (in the absence of anticoagulation) ALT or AST $> 3 \times \text{ULN}$ accompanied by (general) malaise, fatigue, abdominal pain, nausea, or vomiting, or rash, or eosinophilia
Isolated ALT or AST elevation	
Isolated ALP elevation	
 ALT or AST $> 8 \times \text{ULN}$ $5 \times \text{ULN} < \text{ALT/AST} \leq 8 \times \text{ULN}$ $3 \times \text{ULN} < \text{ALT/AST} \leq 5 \times \text{ULN}$ ALP $> 2 \times \text{ULN}$ (in the absence of known bone pathology) Any clinical event of jaundice (or equivalent term) Any adverse event potentially indicative of liver toxicity
Others	

Table 15-2 Actions required for Liver Events

Criteria	Actions required
Potential Hy's Law case	
ALT or AST elevation with coagulopathy	
 Discontinue the study treatment immediately
ALT or AST elevation accompanied by symptoms	
 Hospitalize, if clinically appropriate Establish causality
Isolated ALT or AST elevation $> 8 \times \text{ULN}$	
 Complete CRFs per liver event guidance
Jaundice	
Isolated ALT or AST elevation > 5 to $\leq 8 \times \text{ULN}$	
 If confirmed, consider interruption or discontinuation of study drug If elevation persists for more than 2 weeks, discontinue the study drug Establish causality Complete CRFs per liver event guidance
Isolated ALT or AST elevation > 3 to $\leq 5 \times \text{ULN}$ (patient is asymptomatic)	
 Monitor liver chemistry tests two or three times weekly
Isolated ALP elevation	
 Repeat liver chemistry tests within 48-72 hours If elevation is confirmed, measure fractionated ALP; if $>50\%$ is of liver origin, establish hepatic causality Complete CRFs per liver event guidance
Any AE potentially indicative of liver toxicity	
 Consider study treatment interruption or discontinuation Hospitalize if clinically appropriate Complete CRFs per liver event guidance

Table 15-3 Exclusion of underlying liver disease

Disease	Assessment
Hepatitis A, B, C, E	
IgM anti-HAV; HBSAg, IgM anti-HBc, HBV DNA; anti-HCV, HCV RNA, IgM & IgG anti-HEV, HEV RNA
CMV, HSV, EBV infection	
IgM & IgG anti-CMV, IgM & IgG anti-HSV; IgM & IgG anti-EBV
Autoimmune hepatitis	
ANA & ASMA titers, total IgM, IgG, IgE, IgA
Alcoholic hepatitis	
Ethanol history, γGT, MCV, CD-transferrin
Nonalcoholic steatohepatitis	
Ultrasound or MRI
Hypoxic/ischemic hepatopathy	
Medical history: acute or chronic CHF, hypotension, hypoxia, hepatic venous occlusion. Ultrasound or MRI.
Biliary tract disease	
Ultrasound or MRI, ERCP as appropriate.
Wilson disease	
Caeruloplasmin
Hemochromatosis	
Ferritin, transferrin
Alpha-1-antitrypsin deficiency	
Alpha-1-antitrypsin

16 Appendix 2: Concept1 Platform Inhaler: Instructions for use of medical devices for investigational human use Instructions for using inhaler and capsules

[figure not shown]
Do not swallow capsules.

Follow the instructions below for using your inhaler. You will take the study drug contained within the capsules by inhalation using the inhaler. If you have any questions, please ask the doctor or nurse at the study center.

Your inhaler and capsules

The study drug package consists of both the inhaler and one or more blister-packaged capsules.

[figure not shown]
[figure not shown]
- Capsules are supplied in blisters.
- Inhaler consists of a cap, mouthpiece, and a base

[figure not shown]
[figure not shown]
[figure not shown]
[figure not shown]

[figure not shown]
[figure not shown]
[figure not shown]
Your inhaler is designed to deliver the medicine contained within the capsules.

Do not use study medication capsules with any other capsule inhaler and do not use the inhaler to take any other capsule medicine.

How to use your inhaler

	Pull off cap.
	Open inhaler: Hold the base of the inhaler firmly and tilt back the mouthpiece. This opens the inhaler.
	Prepare capsule: Immediately before use, with dry hands, separate one of the blisters from the blister card by tearing along the perforations and lift the corner of the foil.
	Remove a capsule: Peel away the foil and remove the capsule from the blister.
	Insert capsule: Place the capsule into the capsule chamber. Never place a capsule directly into the mouthpiece.

 6	
Close the inhaler: You should hear a “click” as the mouthpiece closes onto the inhaler base.

 7	
Pierce the capsule:
 
• Hold the inhaler upright with the mouthpiece pointing up.• Pierce the capsule by firmly pressing together both side buttons at the same time. Do this only once.• You should hear a “click” as the capsule is being pierced.
 8	
Release the side buttons fully.

 9	
Breathe out: Before placing the mouthpiece in your mouth, breathe out fully. Do not blow into the mouthpiece.

 10	
Inhale the medicine To breathe the medicine deeply into your airways:
 
• Hold the inhaler as shown in the picture. The side buttons should be facing left and right. Do not press the side buttons.• Place the mouthpiece in your mouth and close your lips firmly around it.• Breathe in rapidly but steadily and as deeply as you can.

	
Note: As you breathe in through the inhaler, the capsule spins around in the chamber and you should hear a whirring noise. You will experience a sweet flavor as the medicine goes into your lungs.
 
Additional information: Occasionally, very small pieces of the capsule can get past the screen and enter your mouth. If this happens, you may be able to feel these pieces on your tongue. It is not harmful if these pieces are swallowed. The chances of the capsule breakage will be increased if the capsule is accidentally pierced more than once (step 7). Therefore it is recommended that you follow the storage directions, remove the capsule from the blister immediately before use and pierce each capsule only once.
 
If you do not hear a whirring noise: The capsule may be stuck in the capsule chamber. If this happens:
 
• Open the inhaler and carefully loosen the capsule by tapping the base of the inhaler. Do not press the side buttons.• Inhale the medicine again by repeating steps 9 to 11.
	
Hold breath: After you have inhaled the medicine:
 
• Hold your breath for at least 5-10 seconds or as long as you comfortably can while taking the inhaler out of your mouth.• Then breathe out.• Open the inhaler to see if any powder is left in the capsule. 
If there is powder left in the capsule:
 
• Close the inhaler.• Repeat steps 9, 10, 11, and 12. 
Most people are able to empty the capsule with one or two inhalations.
 
Additional information: Some people may occasionally cough briefly soon after inhaling the medicine. If you do, don't worry. As long as the capsule is empty, you have received your medicine.

	
After you have finished taking your medicine:
 
• You may be directed by your physician to rinse mouth with water and spit it out; do not swallow the water.• Open the mouthpiece again, and remove the empty capsule by tipping it out of the capsule chamber. Put the empty capsule in your household waste.• Close the inhaler and replace the cap. 
Do not store the capsules in the inhaler.

REMEMBER:

- Do not swallow capsules.
- Only use the inhaler contained in this pack.
- Capsules must always be stored in the blister, and only removed immediately before use.
- Never place a capsule directly into the mouthpiece of the inhaler.
- Do not press the side buttons more than once.
- Never blow into the mouthpiece of the inhaler.
- Always release the push buttons before inhalation.
- Never wash the inhaler with water. Keep it dry. See “How to clean your inhaler”.
- Never take the inhaler apart.
- Always use the new inhaler that comes with your new medication pack. Dispose of each inhaler after the number of uses identified by your physician.
- Do not store the capsules in the inhaler.
- Always keep the inhaler and capsules in a dry place, and avoid very hot or cold temperatures.

How to clean your inhaler

- Clean your inhaler once a week.
- Wipe the mouthpiece inside and outside to remove any powder with a clean, dry lint-free cloth.
- Do not wash your inhaler with water. Keep it dry.
- Do not take the inhaler apart.

Manufactured by:

Novartis Pharma AG, Switzerland

© Novartis
